APPENDIX I: Hematology Oncology Quality of Life Survey – FACT-Br
(Version 4)

Patient MRN: _____

Patient Name: _____

Date/Time of Visit: _____

Patient DOB: _____

Below is a list of statements that other people with your illness have said are important. Please circle one (1) number per line indicating your response as it applies to the past 7 days.

		N o t a t a l l	A l i t t e b i t	S o m e - w h a t b i t	Q u i t e a b i t	V e r y m u c h	
		PHYSICAL WELL-BEING					
	I have a lack of energy	0	1	2	3	4	
	I have nausea	0	1	2	3	4	
	Because of my physical condition, I have trouble meeting the needs of my family	0	1	2	3	4	
	I have pain	0	1	2	3	4	
	I am bothered by side effects of treatment	0	1	2	3	4	
	I feel ill	0	1	2	3	4	

	I am forced to spend time in bed	0	1	2	3	4
	SOCIAL/FAMILY WELL-BEING					
	I feel close to my friends	0	1	2	3	4
	I get emotional support from my family	0	1	2	3	4
	I get support from my friends	0	1	2	3	4
	My family has accepted my illness	0	1	2	3	4
	I am satisfied with family communication about my illness	0	1	2	3	4
	I feel close to my partner (or the person who is my main support)	0	1	2	3	4
	Regardless of your current level of sexual activity, please answer the following question. If you prefer not to answer it, please mark this box and go to the next section.					
	I am satisfied with my sex life	0	1	2	3	4
	EMOTIONAL WELL-BEING					
	I feel sad	0	1	2	3	4
	I am satisfied with how I am coping with my illness	0	1	2	3	4
	I am losing in the fight against my illness	0	1	2	3	4
	I feel nervous	0	1	2	3	4
	I worry about dying	0	1	2	3	4

	I worry that my function will get worse	0	1	2	3	4
FUNCTIONAL WELL-BEING						
	I am able to work (include work from home)	0	1	2	3	4
	My work (include work at home) is fulfilling	0	1	2	3	4
	I am able to enjoy life	0	1	2	3	4
	I have accepted my illness	0	1	2	3	4
	I am sleeping well	0	1	2	3	4
	I am enjoying the things I usually do for fun	0	1	2	3	4
	I am content with the quality of my life right now	0	1	2	3	4
ADDITIONAL CONCERNS						
	I am able to concentrate	0	1	2	3	4
	I have had seizures (convulsions)	0	1	2	3	4
	I can remember new things	0	1	2	3	4
	I get frustrated that I cannot do the things I used to	0	1	2	3	4
	I am afraid of having a seizure (convulsion)	0	1	2	3	4
	I have trouble with my eyesight	0	1	2	3	4

	I feel independent	0	1	2	3	4
	I have trouble hearing	0	1	2	3	4
	I am able to find the right word(s) to say what I mean	0	1	2	3	4
	I have difficulty expressing my thoughts	0	1	2	3	4
	I am bothered by the change in my personality	0	1	2	3	4
	I am able to make decisions and take responsibility	0	1	2	3	4
	I am bothered by my drop in my contribution to the family	0	1	2	3	4
	I am able to put my thoughts together	0	1	2	3	4
	I need help caring for myself (bathing, dressing, eating, etc.)	0	1	2	3	4
	I am able to put my thoughts into action	0	1	2	3	4
	I am able to read like I used to	0	1	2	3	4
	I am able to write like I used to	0	1	2	3	4

	I am able to drive a vehicle (my car, truck, etc.)	0	1	2	3	4
	I have trouble feeling sensations in my arms, hands, or legs	0	1	2	3	4
	I have weakness in my arms or legs	0	1	2	3	4
	I have trouble with coordination	0	1	2	3	4
	I get headaches	0	1	2	3	4

APPENDIX II: Food diary

Date:

APPENDIX III: ECOG Performance Status Scale

ECOG Performance Status Scale	
Grade	Descriptions
0	Normal activity. Fully active, able to carry on all pre-disease performance without restriction.
1	Symptoms, but ambulatory. Restricted in physically strenuous activity, but ambulatory and able to carry out work of a light or sedentary nature (e.g., light housework, office work).
2	In bed <50% of the time. Ambulatory and capable of all self-care, but unable to carry out any work activities. Up and about more than 50% of waking hours.
3	In bed >50% of the time. Capable of only limited self-care, confined to bed or chair more than 50% of waking hours.
4	100% bedridden. Completely disabled. Cannot carry on any self-care. Totally confined to bed or chair.
5	Dead.

APPENDIX IV

	Pre-Treatment Visit #1	Pre-Treatment Visit #2	Pre-Treatment Visit #3	Temodar plus radiation therapy (RT)	Temodar and RT completed	Post-Treatment Visit #1	Post-Treatment Visit #2
	D-28 to day -7	-28 to day -7	D-28 to day -7	Day 0-42	Day42	Appx. Day 70	2-3 months after PTV1
				Weekly	Daily		
Informed Consent	X						
Medical History	X			X		X	X
Concomitant Medications / Treatments	X		X	X		X	X
Physical Exam	X			X		X	X
Vital Signs/Weight/ Waist Circumference	X	X		X		X	X
Lipid profile, CBC with diff, hemoglobin A1C,	X					X	
Serum BHB		X		X		X	X
Complete Metabolic Panel, fasting glucose, fasting insulin		X		X		X	X
Platelet Mitochondrial Labs		X				X	X
MRI		X				X	X
Food diary				X X		X	
	Pre-Treatment Visit #1	Pre-Treatment Visit #2	Pre-Treatment Visit #3	Temodar plus radiation	Temodar and RT completed	Post-Treatment Visit #1	Post-Treatment Visit #2

			ent Visit #3	therapy (RT)			
	D-28 to day -7	-28 to day -7	D-28 to day - 7	Day 0-42	Day42	Appx. Day 70	2-3 months after PTV1
Adverse Events				Weekly	Daily	X	X
Performance Status	X			X		X	X
Quality of Life (FACT-BR)		X		X		X	X
Neurocognitive Testing		X				X	X
RD Consult (initial in person and then via phone)			X	X			
Treatment							
MAD			X	X	X	X	
Temodar and RT (Stupp)				X	X		

APPENDIX V

RANO Criteria for Response Assessment using MRI

From: Wen 2010. **Response**

Complete Response

Criteria

Requires all of the following: complete disappearance of all enhancing measurable and non-measurable disease sustained for at least 4 weeks; no new lesions; stable or improved non-enhancing (T2FLAIR) lesions; patients must be off corticosteroids (or on physiologic replacement doses only); and stable or improved clinically. Note: Patients with non-measurable disease only cannot have a complete response; the best response possible is stable disease.

Partial Response

Requires all of the following: $\geq 50\%$ decrease compared with baseline in the sum of products of perpendicular diameters of all measurable enhancing lesions sustained for at least 4 weeks; no progression of non-measurable disease; no new lesions; stable or improved non-enhancing (T2/FLAIR) lesions on same or lower dose of corticosteroids compared with baseline scan; the corticosteroid dose at the time of the scan evaluation should be no greater than the dose at the time of baseline scan; and stable or improved clinically. Note: Patients with non-measurable disease only cannot have a partial response; the best response possible is stable disease.

Stable Disease

Requires all of the following: does not qualify for complete response, partial response, or progression; stable non-enhancing (T2/FLAIR) lesions on same or lower dose of corticosteroids compared with baseline scan. In the event that the corticosteroid dose was increased for new symptoms and signs without confirmation of disease progression on neuroimaging, and subsequent follow-up imaging show that this increase in corticosteroids was required because of disease progression, the last scan considered to show stable disease will be the scan obtained when the corticosteroid dose was equivalent to the baseline dose.

Progressive Disease

Defined by any of the following: $\geq 25\%$ increase in the sum of the products of maximal perpendicular diameters of enhancing tumor(s) compared to the smaller of pre-SL-701 baseline or best response following initiation of SL-701; New measureable contrast-enhancing lesion(s) defined as lesion(s) that measure at least 1 cm in at least 2 planes; Significant clinical decline not attributable to co-morbid event or change in concurrently administered medication.

NOTE: All measurable and non-measurable lesions must be assessed using the same techniques as at baseline. Abbreviation: FLAIR, fluid-attenuated inversion recovery

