1. OBJECTIVES

- 1.1. Hypothesis/Rationale of the Study: Modified Atkins diet (MAD) concurrent with radiation therapy will produce ketosis and improve outcomes in patients with malignant gliomas due to increased sensitivity of the tumors to radiation therapy.
- 1.2. Primary Objectives
 - 1.2.1. Assessment of feasibility of inducing ketosis with MAD concurrent with radiation therapy by measuring serum beta-hydroxybuterate
 - 1.2.2. Assessment of fasting glucose and insulin levels with MAD concurrent with radiation therapy
 - 1.2.3. Assessment of compliance with MAD concurrent with radiation therapy
- 1.3. Secondary Objectives
 - 1.3.1. Assessment of 6-month progression-free survival in patients with high-grade gliomas with MAD concurrent with radiation therapy as compared to historical controls
 - 1.3.2. Safety of MAD concurrent with radiation and chemotherapy therapy
- 1.4. Exploratory Objectives
 - 1.4.1. Assessment of QOL changes with MAD concurrent with radiation therapy
 - 1.4.2. Assessment of cognitive function changes with MAD concurrent with radiation therapy
 - 1.4.3. Assessment of 2-year survival of patients with high-grade primary brain neoplasms with MAD concurrent with radiation therapy as compared to historical controls
 - 1.4.4. Assessment of mitochondrial respiration in peripheral platelets and correlate with cognitive findings

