10.2. Definitions

10.2.1. **Quality of Life (QOL)**: QOL will be assessed using the FACT-Br QOL tool. See Appendix I. QOL scores pre-intervention will be compared to post intervention-QOL score. QOL will also be obtained at the post-treatment visit #2 to assess if termination of intervention decreased QOL score. We understand that there are many variables that can affect QOL during this time other than the intervention.

10.2.2. **Two-year survival (2YS)**: Duration of survival will be defined as the number of months from diagnosis to death due to any cause.

10.2.3. **6-month progression free survival (6moPFS)**: will be defined as the percentage of patients without progression (defined below) at 6 months.

10.2.4. **Ketosis**: Will be defined as serum BHB ≥ 0.5 mM

10.2.5. **Compliance**: Dietary adherence is assessed by review of the daily food diary (Appendix II) serum ketone levels.

10.3. **Methods for Evaluation of Measurable Disease**: All baseline evaluations should be performed as closely as possible to the beginning of treatment. MRI imaging techniques that can be used to determine progression are:

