10.3.5. T1 post-contrast axial and coronal images

10.4. Response Criteria

10.4.1. Evaluation of target lesions will use the Radiographic Assessment in Neuro-oncology (RANO) criteria. See Appendix V will be defined as by RANO criteria.

10.4.1.1. >5 mm increase in maximal diameter, as well as $\geq 25\%$ increase in the sum of the products of the progressing

10.4.1.2. Significant increase in T2/FLAIR non-enhancing lesion compared with baseline (post-chemoradiation) or best response after initiation of therapy, not caused by comorbid events (e.g., radiation therapy, demyelination, ischemic injury, infection, seizures, postoperative changes, or other treatment effects)

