10.4.1.3. Clear progression of non-measurable disease

10.4.1.4. Any new lesion

10.5 Statistics

10.5.1 Ketosis will be defined as serum BHB > 0.05 mM throughout 6-week period of radiation and chemotherapy. We hope to find that in our given sample of 30 patients at least 50% will meet this criteria. We will compute a 95% confidence interval for this rate to estimate the likely range in the target population. A 10% increase in glutamate within the tumor on the post-RT MRI as compared to the pre-RT MRI will be considered evidence that the tumor is using ketones as fuel by the conversion to glutamate.

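### Progression, the event behind the secondary endpoint 6moPFS, is defined by two differing lists with no stated precedence, and one of them measures growth from an agent that this trial does not give

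*Combined protocol and SAP*

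**What the plan says.** The secondary objective in 1.3.1 is "Assessment of 6-month progression-free survival in patients with high-grade gliomas with MAD concurrent with radiation therapy as compared to historical controls". Section 10.2.3 says that 6moPFS "will be defined as the percentage of patients without progression (defined below) at 6 months".

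The first progression list after that is in 10.4.1, whose lead-in reads, as the text now stands, "See Appendix V will be defined as by RANO criteria". Its items are:
- 10.4.1.1: ">5 mm increase in maximal diameter, as well as" a rise of at least 25% in the sum of products. The sentence then breaks off.
- 10.4.1.2: "Significant increase in T2/FLAIR non-enhancing lesion compared with baseline (post-chemoradiation) or best response after initiation of therapy", with exclusions for other causes.
- 10.4.1.3: "Clear progression of non-measurable disease".
- 10.4.1.4: any new lesion.

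Appendix V, also headed RANO, has its own Progressive Disease entry, met by any one of three items. The first is a rise of at least 25% in the sum of products, "compared to the smaller of pre-SL-701 baseline or best response following initiation of SL-701". The second is a new enhancing lesion that reaches a minimum size. The third is significant clinical decline without another explanation.

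On baseline timing, 10.3 says: "All baseline evaluations should be performed as closely as possible to the beginning of treatment". MRIs are scheduled before radiation, four weeks after it (about Day 70), and at post-treatment visit 2, which Appendix IV places 2 to 3 months after visit 1.

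**The concern.** A proportion free of progression is only as well defined as progression itself. Here a reader who follows 10.4.1 and a reader who follows its pointer to Appendix V would apply different rules to the same patient, and both could say that they had used RANO. A reader who applies Appendix V literally cannot apply its growth rule at all, because the comparator belongs to a different agent. The agent named on the title page is temozolomide, and the intervention is the diet.

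The comparison with historical controls is where this matters. It has no concurrent arm in which the same ambiguity would fall equally, so any difference in the definition goes straight into the result. If the choice of list or reference scan is left until scans have been read, it becomes a post hoc choice.

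**Working it through.** The documents give no expected 6moPFS, historical rate or power figure, so there is no stated number to reproduce. The check is a side-by-side reading, followed by illustrations of size.

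**1. The two lists**

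| Item | 10.4.1 | Appendix V, Progressive Disease |
|---|---|---|
| Size | more than 5 mm **and** at least 25% in product | at least 25% in product alone |
| T2/FLAIR increase | progression (10.4.1.2) | not listed; an increase only rules out stable disease |
| New lesion | any | enhancing, 1 cm or more in two or more planes |
| Non-measurable progression | progression (10.4.1.3) | not listed |
| Clinical decline | not listed | progression |

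Appendix V is looser on size and clinical decline. Section 10.4.1 is looser on new lesions, T2/FLAIR and non-measurable disease. The conflicts run both ways.

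**2. Effect of the list on one lesion**

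Assume a round lesion of diameter d that grows evenly, so the product is d², and one shared reference scan for both rules.
- 20 to 24 mm: (24/20)² − 1 = 44%, and +4 mm. This meets Appendix V's size rule but not 10.4.1.1.
- The rules can disagree where 25% product growth comes before +5 mm, which is below d = 5/(√1.25 − 1) = 42.4 mm.
- At 20 mm, the band of disagreement runs from 25% up to (25/20)² − 1 = 56% product growth.
- Separately, a new 6 mm lesion is progression by 10.4.1.4 but fails Appendix V's new-lesion rule.

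**3. Effect of the reference scan**

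Take the same lesion at 20 mm before radiation, 24 mm at Day 70 and 26 mm at post-treatment visit 2.
- From the pre-radiation scan: (26/20)² − 1 = 69%, +6 mm. Both size rules are met.
- From Day 70: (26/24)² − 1 = 17%, +2 mm. Neither is met.

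**4. Does a Day 70 reference always favour the trial?**

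With growth judged from the smaller of baseline or best response, a product-only rule makes the later reference no smaller, so 6moPFS can only stay or rise. Under the joint rule this fails, because the scan with the smaller product need not have the smaller diameter. Take 30×10 mm before radiation (300 mm²), 20×18 mm at Day 70 (360) and 27×20 mm later (540).
- From pre-radiation: 540/300 − 1 = +80%, but 27 − 30 = −3 mm. Not progression.
- From Day 70: 540/360 − 1 = +50%, and 27 − 20 = +7 mm. Progression.

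**5. Effect on the endpoint**

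With 30 evaluable patients (3.3), each reclassified patient moves 6moPFS by 1/30 = 3.3 points. For scale, at an assumed 15/30 the exact (Clopper-Pearson) 95% interval is 31.3% to 68.7%.

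**The case against.** The best reply is that the documents are less open than they look. The wording of 10.2.3 points forward, and the next list is 10.4.1, so that list is the natural reading. Section 10.1 names RANO as the standard and links the publication. The lead-in to 10.4.1 lacks a subject, so a lost word or heading might have made that list the definition and left Appendix V to response alone. This is a small feasibility study in which response is not primary, and one patient's shift is small beside the sampling error.

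Much of this stands. Reading 10.4.1 as governing is plausible. But the section itself sends the reader to Appendix V, no legible text ranks the two, and a general citation cannot decide between two lists that both claim it. The five differences and the SL-701 wording sit in legible text and do not depend on the broken sentence.

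Two stronger readings are tempting and should be resisted. A reader might infer that 10.4.1.1 names no reference scan; its text breaks off, possibly in PDF reading, so nothing is built on that. A reader might also infer that 10.3 contradicts 10.4.1.2. It does not: 10.3 is a general instruction on when to do baseline evaluations, and the post-chemoradiation baseline in 10.4.1.2 is stated only for T2/FLAIR. What remains is that the reference for enhancing growth is unsettled.

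**Conclusion.** The point holds. The event for 6moPFS has two differing definitions with no stated precedence, and Appendix V's growth rule rests on a comparator that does not exist in this trial. Confidence is high on the textual mismatch. It does not extend to any particular effect on the result: the number of patients affected is unknown, the net direction is unknown, and without a historical rate the effect on that comparison cannot be sized. The illustrations assume round lesions with even growth, except the last lesion example, which is deliberately not round.

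A reader might conclude that 6moPFS is biased upward, or that a Day 70 reference would necessarily make it so. The documents do not support the first, since the list conflicts run both ways. The second is true only under a product-only size rule. No primary objective (ketosis, glucose and insulin, compliance) is affected. The sponsor should correct this, but it does not undermine the feasibility question.

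**What to change.** Before progression is assessed:

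1. Replace both SL-701 references in Appendix V with a reference scan that exists in this trial. Deleting them alone would leave the growth rule with no comparator.
2. Reconcile 10.4.1 and Appendix V into one identical progression list, checked against the RANO publication linked in 10.1, and state that it governs 6moPFS. It should settle the size rule, the new-lesion rule, the place of T2/FLAIR and non-measurable progression, whether clinical decline alone counts, and whether the confirmatory scans mentioned in 10.1 are required before progression is declared.
3. Name one already scheduled MRI as the reference for enhancing growth and one for T2/FLAIR growth, and word 10.3 to agree. The choice is the sponsor's. If Day 70 is chosen for enhancing disease, state that earlier growth does not count by itself and that only one later protocol-scheduled MRI remains (post-treatment visit 2). Add that the choice can only keep or raise 6moPFS if, and only if, a product-only size rule is adopted.

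The cost is an amendment to 10.3, 10.4.1 and Appendix V. Because it fixes the definition of a secondary endpoint, it is more than a typographical correction, and any scan already classified for progression would need re-reading under the single list. No scan is added.

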APPENDIX VI

GBM cognitive protocol (repeated three times)

- 1) Demographic, personal information
 - a) Academic and Medical History Questionnaire
- 2) Executive ability, working memory, attention
 - a) Delis Kaplan Executive Function System, Trails subtest
 - b) Porteus Maze Test [revised version]
 - c) Verbal Primary Memory with Interference
 - d) Auditory Verbal Sequencing Test
 - e) Corsi Block-Tapping Task
- 3) Lexical Access
 - a) Controlled Oral Word Production (phonological & categorical constraints)
 - b) Boston Naming Test
- 4) Secondary (long-term) memory
 - a) Memory Impairment Screen
 - b) Verbal Paired Associate Learning
 - c) California Verbal Learning Test-II
 - d) Spatial Paired Associate Learning
- 5) Mood
 - a) Beck Depression Inventory
 - b) Beck Anxiety Inventory
- 6) Cognitive Symptoms
 - a) Dysexecutive Questionnaire
 - b) Everyday Memory Questionnaire

APPENDIX VII

10/19/2016	The Charlie Foundation - Pain Relievers, Cold & Allergy	10/19/2016	The Charlie Foundation - Pain Relievers, Cold & Allergy
 FeverAll Acetaminophen Suppositories (all strengths) • Actavis	ACTIVE INGREDIENTS: Acetaminophen 500 mg	 Ay Mentholated Vapor Inhaler (Nasal Decongestant) • B.F. Ascher & Co., Inc	ACTIVE INGREDIENTS: Pseudoephedrine HCl 12.5 mg
NOTE: Although glycerol is a main ingredient of this product, the colon converts it to fatty acids; it is not used as sugar therefore it is safe for ketogenic therapy.	INACTIVE INGREDIENTS: Carnauba Wax, Colloidal Silicon Dioxide, D&C Yellow #10 Aluminum Lake, FD&C Red #40 Aluminum Lake, FD&C Yellow #6 Aluminum Lake, Iron Oxide, Magnesium Stearate, Microcrystalline Cellulose, Polyethylene Glycol, Polyvinyl Alcohol, Pregelatinized Starch, Shellac, Sodium Starch Glycolate, Talc, Titanium Dioxide	 Breath Again with SinoMarin - All Natural Seawater Nasal Spray • P.N. GEROLYMATOS	INACTIVE INGREDIENTS: Aromatic Eucalyptus Oil, Menthol and Lavender Oil
ACTIVE INGREDIENTS: Acetaminophen	INACTIVE INGREDIENTS: Glycerol Monostearate, Hydrogenated Vegetable Oil, Polyoxyethylene Stearate, Polysorbate 80	 Neo-Synephrine Nasal Saline Moisturizer Spray • Bayer	INACTIVE INGREDIENTS: Sterilized Seawater 70%, Purified Water 30%. Equivalent to 2.3% of Salt
 Sudafed Nasal Decongestant Maximum Strength, Non-Drowsy 30 mg Tablets • Pfizer	Contains 120mg carbohydrate per tablet	 Sudafed PE Sinus & Allergy Maximum Strength Tablets • Pfizer	INACTIVE INGREDIENTS: Water, Sodium Chloride, Disodium Phosphate, Sodium Phosphate, EDTA Disodium, Benzalkonium Chloride
ACTIVE INGREDIENTS: Pseudoephedrine HCl - 30 mgNasal Decongestant	INACTIVE INGREDIENTS: Carnauba Wax, Colloidal Silicon Dioxide, D&C Yellow #10 Aluminum Lake, FD&C Red #40 Aluminum Lake, FD&C Yellow #6 Aluminum Lake, Iron Oxide, Magnesium Stearate, Microcrystalline Cellulose, Polyethylene Glycol, Polyvinyl Alcohol, Pregelatinized Starch, Shellac, Sodium Starch Glycolate, Talc, Titanium Dioxide	Contains 100mg carbohydrate per tablet	NOTE: Breath Again and Neo-Synephrine are salt solutions for clearing nasal passageways. There are several similar products on the market that may also be used. Check to make sure the ingredients are comparable to these.
ACTIVE INGREDIENTS: (in each Tablet): Chlorpheniramine Maleate (4 mg), Phenylephrine HCl (10 mg).	INACTIVE INGREDIENTS: Colloidal Silicon Dioxide, Crospovidone, Magnesium Stearate, Microcrystalline Cellulose, Pregelatinized Starch, and Stearic Acid	ACTIVE INGREDIENTS: (in each Tablet): Chlorpheniramine Maleate (4 mg), Phenylephrine HCl (10 mg).	ACTIVE INGREDIENTS: Acetaminophen (325 mg), Phenylephrine HCl (3 mg)
INACTIVE INGREDIENTS: Candelilla Wax, Colloidal Silicon Dioxide, Crospovidone, FD&C Yellow No. 6 Aluminum Lake, Hypromellose, Microcrystalline Cellulose, Polyethylene Glycol, Polysorbate 80, Povidone, Pregelatinized Starch, Starch, Stearic Acid, and Titanium Dioxide	INACTIVE INGREDIENTS: Candelilla Wax, Colloidal Silicon Dioxide, Crospovidone, FD&C Yellow No. 6 Aluminum Lake, Hypromellose, Microcrystalline Cellulose, Polyethylene Glycol, Polysorbate 80, Povidone, Pregelatinized Starch, Starch, Stearic Acid, and Titanium Dioxide	INACTIVE INGREDIENTS: (in each Tablet): Chlorpheniramine Maleate (4 mg), Phenylephrine HCl (10 mg).	INACTIVE INGREDIENTS: Candelilla Wax, Colloidal Silicon Dioxide, Crospovidone, FD&C Yellow No. 6 Aluminum Lake, Hypromellose, Microcrystalline Cellulose, Polyethylene Glycol, Polysorbate 80, Povidone, Pregelatinized Starch, Starch, Stearic Acid, and Titanium Dioxide
 Afrin 12 Hour Nasal Spray Original • Schering-Plough HealthCare Products	Contains less than 1000mg carbohydrate per tablet (NOTE: This is much higher than the above pain relievers). ACTIVE INGREDIENTS: Acetaminophen (325 mg), Phenylephrine HCl (3 mg)	 Vicks VapoRub VapORIZING Ointment • Procter & Gamble	INACTIVE INGREDIENTS: Benzalkonium Chloride Solution, Benzyl Alcohol, Edetate Disodium, Polyethylene Glycol, Povidone, Propylene Glycol, Water Purified, Sodium Phosphate Dibasic, Sodium Phosphate Monobasic
ACTIVE INGREDIENTS: Camphor (4.8%), Eucalyptus Oil (1.2%), Menthol (2.6%), Cedarleaf Oil, Nutmeg Oil, Special Petrolatum, Thymol, Turpentine Oil	INACTIVE INGREDIENTS: Camphor (4.8%), Eucalyptus Oil (1.2%), Menthol (2.6%), Cedarleaf Oil, Nutmeg Oil, Special Petrolatum, Thymol, Turpentine Oil	ACTIVE INGREDIENTS: Levmetamfetamine, Bornyl Acetate, Camphor, Lavender Oil, Menthol, Methyl Salicylate	INACTIVE INGREDIENTS: Levmetamfetamine, Bornyl Acetate, Camphor, Lavender Oil, Menthol, Methyl Salicylate
 Vicks VapoInhaler (Nasal Decongestant) • Procter & Gamble	INGREDIENTS: Levmetamfetamine, Bornyl Acetate, Camphor, Lavender Oil, Menthol, Methyl Salicylate	 Afrin 12 Hour Nasal Spray Original • Schering-Plough HealthCare Products	INGREDIENTS: Camphor (4.8%), Eucalyptus Oil (1.2%), Menthol (2.6%), Cedarleaf Oil, Nutmeg Oil, Special Petrolatum, Thymol, Turpentine Oil

Antacids

● Carbohydrate free ▲ Products that contain minimal carbohydrate

▲ **Zantac 150 Maximum Strength Tablets** • Boehringer Ingelheim

131mg Carbohydrate in each tablet

INGREDIENTS: Ranitidine - 75 mg Acid Reducer Hypromellose, Magnesium Stearate, Microcrystalline Cellulose, Synthetic Red Iron Oxide, Titanium Dioxide, Triacetin

▲ **Zantac 75 Tablets** • Boehringer Ingelheim

70mg carbohydrate in each tablet

INGREDIENTS: Ranitidine - 150 mg Acid Reducer Hypromellose, Magnesium Stearate, Microcrystalline Cellulose, Synthetic Red Iron Oxide, Titanium Dioxide, Triacetin

● **Pepto Bismol Liquid – Regular and Maximum Strength** • Procter and Gamble

ACTIVE INGREDIENT: (per tablespoon): Bismuth Subsalicylate (262 mg). (Total Salicylate 130 mg)

INACTIVE INGREDIENTS: Benzoic Acid, D&C Red No. 22, D&C Red No. 28, Flavor, Magnesium Aluminum Silicate, Methylcellulose, Saccharin Sodium, Salicylic Acid, Sodium Salicylate, Sorbic Acid, and Water

▲ **Pepto Bismol Easy To Swallow Caplets Original** • Procter and Gamble

Company reports less than 1gram of carbohydrate in 2 caplets

INGREDIENTS: Bismuth Subsalicylate, Calcium Carbonate, D&C Red No. 27 Aluminum Lake, Magnesium Stearate, Mannitol, Microcrystalline Cellulose, Povidone, Polysorbate 80, Silicon Dioxide, Sodium Starch

▲ **Mylanta**

Mylanta antacid is no longer available in gel caps.

The liquid versions contain 700-900mg of carbohydrate per teaspoon. The chewable tablets are just under 1gm of carbohydrate per tablet.

● **Heather's Tummy Tea - Fennel**

Herbal remedy: traditional digestive aid for colic, heartburn, indigestion, and stomachaches INGREDIENTS: Organic fennel

Warning: Fennel may cause an increase in seizures when used in combination with these drugs: phenytoin (Dilantin); carbamazepine (Tegretol, Carbatrol, Epitol) or oxcarbazepine (Trileptal); gabapentin (Neurontin); valproic acid (Depakene) or divalproex sodium (Depakote); felbamate (Felbatol); tiagabine (Gabitril); levetiracetam (Keppra); topiramate (Topamax); lamotrigine (Lamictal); zonisamide (Zonegran); ethosuximide (Zarontin); and others.

Laxatives

● Carbohydrate free ▲ Products that contain minimal carbohydrate

● **Dulcolax Laxative Suppositories**

INGREDIENTS: Bisacodyl USP 10mg Stimulant Laxative, Hydrogenated Vegetable Oil

● **Fleet Enema Adult • CB Fleet Co, Inc**

ACTIVE INGREDIENTS: Monobasic Sodium Phosphate (19g), Dibasic Sodium Phosphate (7g). Sodium Content: 4.4 g INACTIVE INGREDIENTS: Benzalkonium Chloride, Disodium EDTA, purified water

● **Mineral Oil – There are several brands**

INGREDIENT: Mineral oil

This is an oil that our body does not digest and therefore acts as a laxative (lubricant) in the colon. It should not be taken within 1 hour of medications or vitamin supplements. As with any laxative, it should not be used daily.

● **Miralax • Schering-Plough HealthCare Products, Inc.**

INGREDIENTS: Polyethylene Glycol 3350

IMPORTANT NOTE: This laxative is on the FDA's Watch List for complaints of "neuropsychiatric events". There have also been reports of skin rash (urticaria) with Miralax.

▲ **Senokot Tablets • Purdue Products**

Senokot tablet: 1 tablet has 100mg of carbohydrate Senokot-S: 1 tablet has 110mg of carbohydrate

10/19/2016

The Charlie Foundation - Carb / Non-Carb Ingredients

Carb / Non-Carb Ingredients

Carbohydrate Ingredients	Non-Carbohydrate Ingredients
Glycerin	Asulfamine potassium (AceK)
Maltodextrin	Aspartame
Magnasweet	Carboxymethylcellulose
Organic acids: ascorbic acid, citric acid, lactic acid	Cellulose
Propylene glycol	Hydroxymethylcellulose
Sugars: dextrose, fructose, glucose, lactose, sucrose, sugar, palm sugar, agave nectar, cane syrup, cane juice, corn syrup, honey	Magnesium stearate
Sugar alcohols: erythritol, isomalt, glycerol, manitol, maltitol, sorbitol, xylitol	Microcrystalline cellulose
Starches: cornstarch, hydrogenated starch hydrolysates (HSH), pregelatinized starch, sodium starch glycolate	Polyethylene glycol
	Saccharine
	Superose
	Stevia (rebiana)

<http://www.charlefoundation.org/resources-tools/resources-3/low-carb/item/1137-carbohydrate-non-carbohydrate-ingredients?tmp=component&print=1>

